The wingless (Wnt) signalling protein family is essential for embryogenesis and adult tissue homeostasis. It is emerging that Wnt signalling is a driving force in many disease states including atherosclerosis. Wnt signalling can promote an inflammatory response in monocytes/macrophages (a type of white blood cell) and causes dysfunction of endothelial cells (a type of cell that lines the inner walls of arteries)-keys steps in the development of atherosclerosis. (Blankesteijn *et al.* 2015) Some studies in lung cancer cells and heart muscle cells have shown that IGFBP6 can inhibit the Wnt signalling pathway, illustrating an important interaction between the IGF and Wnt families. (Bach 2016)

Preliminary data from our laboratory studies has established that monocytes from the blood of people with periodontal disease had reduced levels of IGFBP-6 and this reduction can enhance invasion of monocytes into coronary arteries- a key stage in atherosclerosis. Furthermore, we looked at proteins that can be influenced by IGFBP-6 and saw significantly enhanced levels of Egr1 in monocytes from people with periodontal disease compared to the levels detected in healthy controls. Egr1 is a protein that can be activated as a result of infection and plays a role in the pathophysiology of atherosclerosis (Blaschke *et al.*2004).

We have also identified that Wnt proteins in patients with periodontal disease are enhanced compared to controls. A preliminary analysis demonstrated that NOTUM, an antagonist of Wnt signalling, was decreased in both the plasma and monocytes from patients with periodontal disease. These changes in Wnt signalling may promote atherosclerosis in people with periodontal disease.

The main benefit of this research will be a fuller understanding of the pathogenesis between periodontitis and atherosclerosis, and in the longer-term, the identification of new treatments and biomarkers, for better diagnosis, management, and life quality for patients. The findings will be transferrable to other inflammatory conditions, such as stroke, diabetes mellitus, and rheumatoid arthritis.

Study Aim & Objectives

Aim:

The aim of this study is to determine if the monocytes from people with periodontal disease behave differently from those taken from healthy individuals in a way that heightens the risk of atherosclerosis. We will test the hypothesis that reduced levels of IGFBP-6 and altered Wnt signalling contribute to altered monocyte/macrophage pro-atherosclerotic behaviour in patients with periodontitis. Consequently, modification of IGFBP-6 and/or Wnt signalling will retard atherosclerosis and IGFBP-6, and Wnt signalling proteins will act as suitable biomarkers of atherosclerosis disease progression.

Objectives and methods:

- 1. To determine the underlying mechanism of regulation in monocytes/macrophages from people with periodontal disease compared with healthy controls we will assess four key stages that are essential for the development of atherosclerosis, mainly:
 - a. *Monocyte adhesion to endothelial cells:* human monocytes will be isolated using standard techniques. They will be labelled with calcein-AM for 30 minutes, and then incubated with a monolayer of cultured human coronary artery endothelial cells purchased from Promocell.

After 30 minutes the number of adherent monocytes will be quantified by image analysis.

b. *Invasion/Migration assays*: isolated human monocytes will be differentiated into macrophages by culture with 20ng/ml M-CSF for 7 days. Macrophages will be cultured in

Matrigel-coated transwells with 50ng/ml MCP-1 as chemoattractant in the lower chamber. After 72 hours, the number of migrated macrophages will be quantified by image analysis as described previously

c. *Phenotype of macrophages*: macrophage phenotype will be assessed by quantification of M1 (iNOS, IL-6) and M2 (arginase, IL-10) markers by Western blotting and ELISAs.

d. Lipid content of macrophages: Monocyte/macrophages will be incubated with 10µg/ml ox-LDL for 24 hours. Lipid content will be quantified by oil red O staining.
Endocytosis will be quantified using zymosan bead. Changes in RNA will be assessed using qPCR.

The *in vitro* experiments have been designed to determine the effect of increasing or decreasing the level of IGFBP6 and Wnt signalling using various approaches outlined in Table I below.

Ехр	Group 1	Group 2	Group 3	Experimental Question
A	Control + siRNA control	Control + BP6 siRNA	Periodontitis + siRNA control	Does silencing BP6 in control cells mimic efforts observed in cells from periodontal patients?
В	Control + IgG control	Control + BP6 Nab	Periodontitis + IgG control	Does neutralizing IGFBP6 in control cells mimic effects observed in cells from periodontal patients?
С	Control + vehicle	Periodontitis + vehicle	Periodontitis + BP6	Does addition of IGFBP6 to cells from periodontal patients mimic control cells?
D	Control + vehicle	Periodontitis + vehicle	Periodontitis + ETC-159	Does inhibition of Wnt secretion (using ETC-159) in cells from periodontal patients mimic control cells?
E	Control + vehicle	Periodontitis + vehicle	Periodontitis + iCRT	Does inhibition of Wnt/b-catenin signalling (using iCRT) in cells from periodontal patients mimic control cells?
F	Control + vehicle	Control + 400ng/ml Wnt3a	Periodontitis + vehicle	Does treatment of control cells with Wnt3a mimic cell from periodontal patients?

Table I: summary of the design of in vitro experiments

2. Assessing the potential use of IGFBP6 and Wnt proteins as suitable biomarkers

a) Peripheral blood and saliva will be collected from patients with periodontal disease both pre and post treatment and age and gender matched healthy controls. b) Saliva samples will be collected from people with severe periodontitis and age and gender matched controls.

The seven Wnt proteins and IGFBP6 identified by our previous proteomic analysis will be quantified in plasma, isolated monocytes and saliva, and the levels in patients and controls statistically compared. Standard laboratory techniques including western blot and specific enzyme-linked immunosorbent assays (Bio-Plex, Bio-Rad Laboratories Ltd. Hertfordshire, UK) will be used to assess for changes.

This will determine whether IGFBP6 and/or any of the seven Wnt pathway proteins are associated with periodontitis and could lead to future work investigating the role of these proteins in disease progression. Is it likely that other novel findings will be identified and scope to explore these will be undertaken under the current protocol.

See protocols 1-3.

Study sites

 University Hospitals Bristol and Weston NHS Foundation Trust ,[name]

Translational Health Sciences, Research Floor, Level 7, University of Bristol, Bristol Royal Infirmary, [name] (location of laboratory and storage location for samples)

Participants and recruitment

Clinicians or a member of the dental team at the University of Bristol Dental School will approach participants who are attending the hospital for either periodontal assessment or regular dental appointments (healthy volunteers).

- Potential donors will be provided with the same participant information leaflet (see enclosed) containing information about the research. Sufficient time will be provided to participants prior to
- Written consent will be obtained from participants to allow for a basic periodontal examination, and collection of a blood sample. Every 5th person will be asked to provide a sample of saliva.

Inclusion/exclusion criteria for people with periodontitis

Inclusion:

- All people over the age of eighteen (18)
- Capacity to consent
- Attending a scheduled dental appointment at the University of Bristol Dental Hospital
- People with unstable severe periodontitis or a high susceptibility to periodontitis (as defined by the British Society of Periodontology 2019 implementation of the 2017 World Workshop Classification of periodontal and peri-implant diseases and conditions: Stage III/IV and Grade C.)
- At least 18 erupted teeth

Exclusion

- All people under the age of eighteen (18)
- Those who lack capacity to consent
- History of cardiovascular disease such as hypertension, angina, previous myocardial infarction, heart failure, aortic disease, arrhythmia, heart valve disease.
- History of autoimmune/autoinflammatory diseases such as Sjogren's syndrome,
 - rheumatoid arthritis, inflammatory bowel disease, systemic lupus erythematosus, or systemic sclerosis
- History of endocrine disease including diabetes mellitus types 1 and 2
- Currently taking antibiotics or has had antibiotics in the preceding 6 months
- People taking statins, non-steroidal anti-inflammatory medications, immunosuppressive medications or corticosteroids.
- Smokers of tobacco (including Vaping/e-cigarettes)
- History of salivary gland disease or oral mucosa disease

Inclusion/exclusion criteria for healthy volunteers

Inclusion:

- All people over the age of eighteen (18)
- Capacity to consent
- Attending a scheduled dental appointment
- People with no evidence of periodontitis
- At least 18 erupted teeth

Exclusion

- All people under the age of eighteen (18)
- Those who lack capacity to consent
- History of cardiovascular disease such as hypertension, angina, previous myocardial infarction, heart failure, aortic disease, arrhythmia, heart valve disease
- History of autoimmune/autoinflammatory diseases such as Sjogren's syndrome,
 rheumatoid arthritis, inflammatory bowel disease, systemic lupus erythematosus, or
 systemic sclerosis
- History of endocrine disease including diabetes mellitus types 1 and 2
- Currently taking antibiotics or has had antibiotics in the preceding 6 months
- People taking statins, non-steroidal anti-inflammatory medications, immunosuppressive medications or corticosteroids.
- Smokers of tobacco (including Vaping/e-cigarettes)
- History of salivary gland disease or oral mucosa disease

Ethical Considerations and information

Blood and saliva samples will be collected from participants who are capable of informed decision making. Treating clinicians or an appropriately qualified member of their team will obtain informed consent from participants. In general terms, participants will be asked to provide a sample of blood and saliva that will be used in this study to better understand the link between periodontal disease and atherosclerosis. Participant information leaflets and consent forms will be provided (see enclosed).

Sample Collection

Objective 1 and 2b

Upon obtaining consent, the clinical practitioner will collect two tubes of peripheral blood (approximately 20mls in total) from the forearm of the person using standard venepuncture techniques.

The clinical practitioner will ask every 5th person to provide a saliva sample. Whole saliva will be collected in polypropylene vials using the passive drool method (2mls in total). The person will undergo a basic periodontal screen to assess gum health using the previously validated 'Basic Periodontal Exam' (BPE)/ 'Periodontal Probing Depth', as well as recording if there is 'bleeding on probing'. (Dietrich *et al.* 2019). The exam and collection of samples will occur before dental treatment begins. After blood and saliva has been collected, and the periodontal screen performed, the person will have no further participation in the study.

Objective 2a

Upon obtaining consent, the clinical practitioner will collect two tubes of peripheral blood (approximately 20mls in total) from the forearm of the person using standard venepuncture techniques, and saliva will be collected (2mls in total).

The person will undergo a basic periodontal screen to assess gum health using the previously validated 'Basic Periodontal Exam' (BPE)/ 'Periodontal Probing Depth' as well as recording if there is 'bleeding on probing'. (Dietrich *et al.* 2019)

The person will then undertake their routine dental treatment. The time it takes for the successful completion of dental treatment varies, as do the number of necessary appointments, but typically it can take approximately 24 weeks. On completion of this dental treatment the person will be asked to provide one additional peripheral blood sample (approximately 20mls) and saliva (2mls in total) sample. After this second sample of blood and saliva has been collected these participants will have no further participation in the study.

For all the objectives listed above, the clinical practitioner will then anonymise all samples by allocating a code to the samples. Only the clinical practitioners will have access to the code that links the samples and people, not the researchers. Once anonymised, samples will be made available to the researchers, who will analyse the samples using established laboratory techniques as mentioned above.

Duration of participant involvement

Objectives 1 and 2b: participants will be actively involved in the study for approximately 20 minutes at their assessment appointment.

Objective 2a: from the time of their assessment appointment to the successful completion of their dental treatment, the participants will have taken part in the study for approximately 24 weeks. The total amount of time the participant will be actively involved in the study will be approximately 35 minutes, spread over the two appointments.

Sample size determination

From our previous data with similar experimental design and analyses, we have calculated the sample size (**power analysis**) using an online sample size calculator (https://clincalc.com/stats/samplesize.aspx) and p<0.005

Objective 1: Mechanism of regulation

Approximately 150 gum disease (severe periodontitis) participants and 150 control participants (good gum health) will be approached. From these approaches we hope to obtain samples of blood from 125 severe periodontitis and 125 control participants. The sample size is based on previously published studies and our own previous work, and shown to provide a 90% power to detect a 50% change. (Willi *et al.* 2014; Nanbara *et al.* 2012)

Objective 2: Biomarker potential

a) Approximately 20 gum disease (severe periodontitis) participants and 20 control participants (good gum health) will be approached. From these approaches we hope to obtain samples of blood and saliva from 12 severe periodontitis and 12 control participant The sample size is required to provide >90% power to detect a 30% change in protein expression.

b) Approximately 30 gum disease (severe periodontitis) participants and 30 control participants (good gum health) will be approached. From these approaches we hope to obtain saliva samples from 20 people with severe periodontitis and 20 control participants
 The sample size is required to provide a 80% power to detect a 20% change. (Jasim *et al.* 2018)

Analysis

Data will be analysed by t-tests when two groups are compared or by ANOVA if more than two groups are assessed.

Withdrawal of participants

Participants will be informed that they can withdraw from the study at any stage- no reason needs to be provided. Withdrawal from the study will not affect their dental care.

Any blood and saliva donated by a participant is a gift, and any samples or data collected up until the point the participant wants to withdraw will be kept, used and included in analysis.

Safety and adverse events

There is minimum risk to taking blood from participants. All clinical study procedures will be carried out on clinics at Bristol Dental Hospital by appropriately trained staff. All cross infection controls will be implemented including those related to COVID 19. All study material is participant specific and all clinical study staff are trained in Good Clinical Practice (GCP). All procedures are performed by clinical staff that have appropriate qualifications and training.

A slight discomfort and bruising may be experienced due to withdrawal of blood. There should be no major adverse effects, pain, discomfort, distress, intrusion, inconvenience or changes to lifestyle as this is a routine blood donation of small volume. No adverse effects are associated with collecting saliva.

Any adverse events should be reported to [name] who will review, record and if necessary, report all events to the UHBW R&I office via the University Hospitals Bristol and Weston adverse event reporting system (UHBW undertake this role on behalf of the Sponsor).

Data management

Confidentiality:

The link between the participant and their coded tissue and periodontal score will be held by the clinical care team. Initially recorded on paper, the link between participants and the code will be transferred to a password-protected University computer. Paper copies of the code will be destroyed securely using NHS confidential waste streams. The researchers will not have access to the code.

Storage and use of data after the study:

Anonymised study data will be stored on the University Research Data Storage Facility (RDSF) and analysed by the researchers. The RDSF is a secure facility that is backed up daily. Access is granted by the University Data Steward at the request of the project Chief Investigator, and will be restricted to members of the research team. After the study, with the consent of the participant, research data will be made available as "open data" on the data.bris Research Data Repository. This means the data will be publicly available and so able to be used by other researchers to support additional research in the future. All data relating to participants will be anonymised and so it will not be possible to identify participants from these data.

Consent forms (hard copies) will be kept in a locked cabinet in a locked office within the dental clinical trials unit. Only dental clinical trials team members have access to this space. They will also be scanned onto University of Bristol electronic storage space which is protected by the University's firewall and is password protected. Consent forms will be held until the blood/saliva is used up or disposed. The researchers using the blood/saliva are in a separate building and will not have access to the paper consent forms, or be able to access the electronic scanned copies.

Auditing and inspection:

The University of Bristol has an arrangement with University Hospitals Bristol and Weston NHS Foundation Trust such that they monitor studies sponsored by the University of Bristol.

Sponsorship

University of Bristol is the Research Sponsor

Insurance

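### Table I requires disease group to be known when Objective 1 cultures are set up, but no masked reading is specified for the cell counts and oil red O lipid.

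*Protocol*

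**What the plan says.** **Readouts.** Under Objectives and methods, item 1a counts adherent cells: "After 30 minutes the number of adherent monocytes will be quantified by image analysis". Item 1b counts migrated cells: "After 72 hours, the number of migrated macrophages will be quantified by image analysis as described previously". Item 1d measures lipid: "Lipid content will be quantified by oil red O staining". Item 1c is of another kind: "macrophage phenotype will be assessed by quantification of M1 (iNOS, IL-6) and M2 (arginase, IL-10) markers by Western blotting and ELISAs".

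**Conditions.** Table I ties each active condition to one disease group. In experiments A, B and F, the BP6 siRNA, the neutralising antibody and Wnt3a go to control cells only. In C, D and E, BP6, ETC-159 and iCRT go to periodontitis cells only (for E the third group is "Periodontitis + iCRT"). The questions have the same form: "Does silencing BP6 in control cells mimic efforts observed in cells from periodontal patients" for A and "Does addition of IGFBP6 to cells from periodontal patients mimic control cells" for C.

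**Coding.** Sample Collection says that samples are coded before they reach the laboratory: "Only the clinical practitioners will have access to the code that links the samples and people, not the researchers". Data management, under Confidentiality, adds that the clinical care team holds the link to the coded tissue and the periodontal score, and that researchers cannot see the code.

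**The concern.** A laboratory comparison of diseased and healthy donors is exposed to expectation bias when the reader knows the group and the readout leaves room for judgement, such as which fields to image, what counts as adherent or migrated, and where to set a stain threshold. Here the expected direction is declared in advance. The protocol's background reports that reduced IGFBP-6 enhances monocyte invasion, and the aim hypothesises pro-atherosclerotic behaviour in patients' cells.

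A systematic reading shift moves the group means themselves. The t-tests and ANOVA in the Analysis section cannot separate it from biology. Recruiting 125 donors per group narrows the interval around the biased value and leaves the bias in place. At stake are the adhesion, migration and lipid comparisons, which are three of the four stages that Objective 1 sets out to assess.

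**Working it through.** **Step 1. Who must know the group?** Every experiment in Table I has one active condition, and that condition goes to one disease group:

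| Exp | Active condition | Cells that receive it |
|---|---|---|
| A | BP6 siRNA | control only |
| B | BP6 neutralising antibody | control only |
| C | BP6 | periodontitis only |
| D | ETC-159 | periodontitis only |
| E | iCRT | periodontitis only |
| F | Wnt3a | control only |

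None of the six can be set up without knowing each donor's group. This follows from the design and does not depend on how the study is conducted.

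**Step 2. Does the coding mask the group?** Sample Collection describes it as anonymisation, and Data management places it under Confidentiality. There are two possible readings:
- If it hides identity only, the group is open in the laboratory.
- If it also hides the group, Table I cannot be carried out as written.

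Either way, the protocol does not say how researchers without the code learn the group, or where that knowledge stops.

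**Step 3. Is reading masked?** For 1a, 1b and oil red O in 1d, the protocol names the technique only. It gives no masked reader, no automated count, and no rule for fields or thresholds.

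**Step 4. The plan's own figure.** Sample size determination gives 125 per group, 90% power, a 50% change and p<0.005, with no SD. The figure therefore cannot be reproduced directly. Solved backwards (two-sided, normal approximation), the detectable standardised difference is (2.807 + 1.282) × √(2/125) = 4.089 × 0.1265 = 0.517. For a 50% change this implies a coefficient of variation of 0.5/0.517, about 97%. The present point does not depend on this figure.

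**Step 5. Illustration of size.** Assumptions, none of which is in the documents:
- no true difference between groups;
- a systematic reader shift of b SD between groups;
- a two-sided two-group t-test;
- all 125 donors per group contributing to the readout.

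The test statistic then follows a noncentral t with 2 × 125 − 2 = 248 degrees of freedom and noncentrality b × √(125/2) = 7.906 × b. The critical values are 1.970 (p<0.05) and 2.832 (p<0.005).

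| Shift b (SD) | Noncentrality | False positives, p<0.05 | False positives, p<0.005 |
|---|---|---|---|
| 0 | 0 | 5% | 0.5% |
| 0.1 | 0.79 | 12.4% | 2.2% |
| 0.2 | 1.58 | 35.0% | 10.8% |
| 0.3 | 2.37 | 65.6% | 32.5% |

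A normal approximation gives nearly the same: 12.4%, 35.3% and 66.0% at p<0.05, and 2.2%, 11.0% and 33.2% at p<0.005. Because the noncentrality grows with the square root of the number per group, a larger sample makes a biased reading more likely to reach significance.

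**The case against.** The strongest reply is that the protocol is silent on reading, and silence is not a statement that reading is open. A reader might infer that the readouts are unmasked, or that the person who plates the cells also chooses fields and thresholds. The documents support neither inference. Table I fixes what the person setting up the cultures must know and says nothing about who reads. The migration assay refers to a previously described method, and the flow charts are not shown. Either could contain a field-selection rule or a labelling step. This stands, and it limits the point to an unspecified safeguard.

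The coding could also be read as partial masking, because it withholds the code and the periodontal score link from researchers. That holds for identity and score. It cannot hold for disease group at culture set-up, and no text carries it through to reading.

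A reader might extend the concern to the whole of items 1a to 1d. ELISA and qPCR depend much less on a reader's judgement, and no argument is made here for the blots.

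Finally, the illustration rests on assumed shifts. It also simplifies the design: Table I has three groups per experiment, for which the Analysis section specifies ANOVA, and 125 per group is given for Objective 1 as a whole and not for each readout. The percentages therefore show sensitivity and do not predict this study's error rate.

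**Conclusion.** The point holds in a limited form. Knowledge of disease group at culture set-up is unavoidable under Table I, the coding is written as confidentiality, and no masked reading or fixed reading rule is specified for adherent monocytes, migrated macrophages or oil red O lipid. The documents do not show that bias will occur.

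If these endpoints are read with the arm visible, expectation bias cannot be distinguished from the hypothesised effect, and sample size gives no protection. Under the stated assumptions, even a 0.1 SD shift raises false positives about fourfold at the protocol's p<0.005 (2.2/0.5 = 4.4), and a 0.2 SD shift about twentyfold (10.8/0.5 = 21.6).

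The change is worth making because it is cheap and leaves Table I untouched. It should be in place before reading starts, since images already read with the arm visible would have to be read again.

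**What to change.** Add to Objectives and methods, with a cross-reference from Sample Collection:

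- Disease group is released to the laboratory for culture set-up only. State who releases it and to whom, so that the coding text and Table I agree.
- After the assay, images and stained wells from 1a, 1b and the oil red O part of 1d are relabelled with a random ID that carries neither group nor condition, for example by a file-renaming script.
- Fields and thresholds follow a rule set in advance and applied under that ID.
- The key is merged only after the readouts are locked.

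If the referenced migration method or a laboratory procedure already contains these steps, citing it explicitly for all three readouts is enough.

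**Cost.** A small relabelling and key-holding step, with no extra samples. Because a script can do the relabelling, no extra reader should be needed. The documents do not describe laboratory staffing, so the team must decide who holds the key.

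### Table I asks whether treated cells 'mimic' the other group, but the only test stated for three groups, ANOVA, does not answer that question

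*Protocol*

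**What the plan says.** Under Objective 1, Table I of the protocol sets out Experiments A to F. Each has three groups: untreated control cells, untreated periodontitis cells, and one of these two cell types after a manipulation of IGFBP6 or Wnt signalling.

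- Three experiments manipulate control cells and take periodontitis cells as the target: A ("Does silencing BP6 in control cells mimic efforts observed in cells from periodontal patients"), B ("Does neutralizing IGFBP6 in control cells mimic effects observed in cells from periodontal patients") and F ("Does treatment of control cells with Wnt3a mimic cell from periodontal patients").
- Three manipulate periodontitis cells and take control cells as the target: C ("Does addition of IGFBP6 to cells from periodontal patients mimic control cells"), D ("Does inhibition of Wnt secretion (using ETC-159) in cells from periodontal patients mimic control cells") and E ("Does inhibition of Wnt/b-catenin signalling (using iCRT) in cells from periodontal patients mimic control cells").

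The text introducing the table says that the experiments are "designed to determine the effect of increasing or decreasing the level of IGFBP6 and Wnt signalling". The Analysis section is one sentence: "Data will be analysed by t-tests when two groups are compared or by ANOVA if more than two groups are assessed". Under Sample size determination, Objective 1 has 125 participants per group, stated to give 90% power to detect a 50% change, with p<0.005 given for the calculations. The protocol does not define 'mimic'.

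**The concern.** To say that treated cells mimic a target group is to say two things: that treatment moved them away from untreated cells of the same type, and that they ended up like the target. The overall F-test asks only whether all three means are equal, so it can be significant purely because periodontitis and control cells differ. A pairwise difference test can support the first part of the claim. No difference test can establish the second, because failing to find a difference is not evidence of similarity.

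The mechanistic conclusion of Objective 1, that IGFBP6 or Wnt signalling contributes to the periodontitis phenotype, is tested through these six questions across several read-outs (adhesion, invasion, phenotype, lipid content). If question and test do not match, the data could be reported as supporting that conclusion, or not, for reasons unrelated to what the treatment did.

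**Working it through.** **Inputs from the protocol.** 125 per group, 90% power, p<0.005 (Sample size determination, Objective 1); three groups per experiment (Table I); ANOVA (Analysis).

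**Assumptions.** Two-sided tests (sidedness is not stated), equal SDs, and all 125 donors per group used in an experiment. The protocol does not say how donors are allocated to experiments.

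**The plan's own figure.** The 125 per group cannot be reproduced, because no SD is given for the 50% change. It can be inverted.
- Normal approximation: d = (2.807 + 1.282) × √(2/125) = 0.517 SD, so a 50% change implies a coefficient of variation of 0.50/0.517 = 97%.
- Exact noncentral t: d = 0.521 SD. This is the periodontitis-control gap used below.

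**1. Overall F when the treatment does nothing.** The three means are 0, d, d (or 0, 0, d). Their squared deviations from the grand mean sum to (2/3)d².
- Noncentrality = 125 × (2/3) × 0.521² = 22.6.
- Critical F(2, 372) at 0.005 = 5.37, so F is significant 94% of the time with independent groups.
- When treated and untreated cells come from the same donors, simulation gives 92% at a within-donor correlation of 0.5 and 91% at 0.8. The range is about 90 to 95%.

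A treatment that closes the gap completely gives means 0, d, 0, and again (2/3)d². With independent groups, F is therefore exactly as likely to be significant for a perfect treatment as for a useless one.

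**2. Treated versus target when half the gap is closed.** The residual difference is 0.521/2 = 0.2607 SD.
- Noncentrality = 0.2607 × √(125/2) = 2.061.
- At 0.005 the critical t on 248 df is 2.832: P(non-significant) ≈ Φ(2.832 − 2.061) = 78%.
- At 0.05 the critical t is 1.970: P(non-significant) ≈ Φ(1.970 − 2.061) = 46%.
- Sensitivity: 74% if the calculation was one-sided at 0.005; 63% if both sizing and testing were two-sided at 0.05.

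**3. Gain from pairing treated with untreated cells.** Take a shift of half the gap, n = 125, alpha 0.005 and an assumed within-donor correlation of 0.5 (normal approximation).
- Paired: SD of the difference = √(2 × (1 − 0.5)) = 1, so the statistic is centred on 0.2607 × √125 = 2.914. Power = Φ(2.914 − 2.807) = 54%.
- The same data analysed as independent groups: power = Φ((2.061 − 2.807)/√0.5) = 15%.

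**4. Could the sample support an equivalence claim?** Take a margin of half the gap and truly equal means. SE = √(2/125) = 0.1265, so margin/SE = 2.061. P(95% CI inside the margin) = 2Φ(2.061 − 1.960) − 1 = 8%.

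**The case against.** The strongest reply is that the protocol commits none of these errors in so many words.

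- **No stated rule.** A reader might infer that a non-significant treated-versus-target difference would be declared mimicry. No sentence says so, and that inference should not be attributed to the investigators. This stands.
- **ANOVA is more than the overall F.** A reader might infer that ANOVA cannot help at all. Every experiment contains the untreated cells of the same type and the target group, so contrasts within the ANOVA can show a shift towards the target. That fits the stated purpose of determining the effect of raising or lowering IGFBP6 and Wnt signalling. This stands. What ANOVA cannot show is that treated and target cells are alike.
- **Contrasts may be in an SAP.** One may exist and is not shown, so the absence of contrasts or a margin is not the finding. But both the questions and the test are fixed in the protocol, and they do not match.
- **The 78% isolates one comparison.** A careful analyst would first want the periodontitis-control gap to be significant. Requiring that as well, simulation under the same assumptions gives about 67 to 69% at 125 per group, still most of the time.
- **Small experiments.** Sharing donors equally over six experiments (about 21 per group) would raise the 78% and 46% to 98% and 87%. The protocol describes no such split. At 21 per group the gap itself would be found only about 11 to 12% of the time at 0.005, so gap found with no treated-versus-target difference would occur in only about 10%. The larger figures are not relied on here.

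**Conclusion.** The point holds as a mismatch between question and test. All six questions ask about mimicry. The stated three-group test is significant about 90 to 95% of the time when the treatment is inert, and a non-significant treated-versus-target comparison would follow 78% of the time (46% at p<0.05) when only half the gap is closed. These figures rest on the 0.52 SD gap inferred from the protocol's own sample size, two-sided testing, and the use of all 125 donors per group.

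The documents do not support saying that the investigators will treat non-significance as mimicry, or that the design cannot answer a useful question. It can show a shift. These are mechanistic laboratory experiments, so what is at stake is the soundness of the Objective 1 conclusion. The correction is cheap and worth making before the data are analysed.

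**What to change.** In the Analysis section, and in the wording of Table I:

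1. Make treated versus untreated the main contrast in each experiment, paired within donor where the same donor's cells are split: within control donors for A, B and F, within periodontitis donors for C, D and E.
2. Report the proportion of the periodontitis-control gap that is reproduced (A, B, F) or reversed (C, D, E), with a 95% CI that reflects uncertainty in both the shift and the gap. Do this only where the gap is itself shown, since the ratio is otherwise unstable.
3. Reword 'mimic' as 'shift towards' the target group.
4. State that a non-significant treated-versus-target difference is not evidence of mimicry.

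The cost is a little more analysis, and some experiments will be reported as a partial or undemonstrated shift. No extra donors are needed. An equivalence margin is not proposed: with 125 per group, a margin of half the gap would be met only about 8% of the time even with equal means, so a formal equivalence claim would need a larger study or a wider margin.
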